The sample size, N=252, was chosen to provide sufficient power for analyses associated with the defined primary outcomes and accounting for 20% attrition. In the absence of normative data, based on results of prior studies among emergency department enrolled PWUO that indicate modest uptake of MOUD (~5%¹⁹¹), and completing referrals to MOUD services (~25%¹⁹²⁻¹⁹⁴), we compute the power to detect significant effects. Using these estimates as the baseline, we anticipate that interactive texting will increase completing referrals to primary care from 25% to 35% ¹⁹⁵⁻¹⁹⁷. The combination of interactive texting and PRC support will enhance time to completing referrals to primary care from 25% to 45%. These anticipated changes indicate odds ratios for intervention versus TAU (effect size) of between 1.5 to 2.0 for OUD-related outcomes. We use these estimated odds ratios (ORs) as the proxy for the rate in treatment versus the control. Evidence from methodological studies assert a useful equivalence involving the hazard ratio (HR), such that when the PH assumption is reasonable, the HR is equivalent to the odds that a randomly chosen person with hazard represented in the numerator will experience the event of interest before a randomly chosen person with hazard represented in the denominator 198-200. The power to detect these effects with α =0.05 (two-tailed) using log-rank comparisons for survival outcomes via the power procedure in SAS v9.4 is ~80%.

Enrollment, Consent and Workflow

Over a 2-year period, Black / Latinx PWUO (N=252) identified in the ED or community by the study team using the electronic medical records (EMR) or self-report will be screened and enrolled by the study team. Specifically, ED-recruited Black and Latinx PWUOs with a positive urine toxicology per the Hospital EMR or self-reporting illicit opioid use among PWUO approached in community settings and confirmed with random saliva toxicology testing will be enrolled over a 2-year period. Community-recruited PWUO participants will complete enrollment in the in private conference rooms located in Lincoln Hospital or START Treatment and Recovery centers or in the NYS OMH Harlem field office site. Given the ethical importance to expand enrollment of vulnerable and hard-to-reach persons living with substance use, including women, unstably housed, and uninsured adults, we will provide reimbursement for peer-driven recruitment (\$25, max 3 referrals per participant).

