Participants randomized to TAU will receive similar payments at the same time points as participants in the intervention arm-1 and arm-2 groups. At the completion of each of the follow-up sessions all participants are compensated for their time.

Proposed Analyses

Aim 1 is a 3-year RCT involving community and ED-enrolled Black / Latinx PWUO who will be screened and enrolled (N=252) **Primary outcomes** will be based on remote and/or in-person follow-up assessments at 3-, 6-, and 12-months and consists of self-reported linkage to primary care-based OUD services (i.e., time to initial receipt of buprenorphine in primary care). **Secondary outcomes** include durability of treatment effect at 52 weeks (e.g., continuous retention in OBOT with buprenorphine), receipt of social services, and longitudinal engagement with the proposed intervention (up to 26 weeks).

Our primary hypothesis is that the rate of linkage to OBOT, i.e., time to first buprenorphine prescription, will be highest among PWUO participants randomized to texting + PRC, followed by those randomized to texting only, then to TAU. To assess this hypothesis, we will utilize Cox proportional hazards (PH) regression to investigate differences in time to service linkage (in days) by intervention group. Cox PH regression is a method for investigating the effect of several variables on the time to a specified event¹⁷⁰. Cumulative hazards functions for the intervention groups will be examined using Nelson-Aalen plots and use the supremum test which uses martingale residuals to check the proportional hazards assumption. If the assumption is violated such that there is no difference in the direction of the association but there is variation in the magnitude of the association, i.e., the hazards ratio (HR) changes over time, then the coefficient that we estimate for that covariate is akin to an 'average effect' over timepoints that are observed in a dataset and the Cox PH model will perform moderately. If the hazards cross, i.e., a change in the direction of the association, the Cox PH model will perform poorly, and we will extend the Cox model to allow for nonproportional hazards using time dependent covariates. Intervention group as assigned will be the sole explanatory variable in the models (see **Methodological Considerations and Alternatives**).

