Intervention fidelity is an important consideration with "real world" research interventions. Lack of fidelity can increase the possibility of a type I or II error and make study findings difficult to interpret. Certain study design considerations are incorporated to support intervention fidelity, e.g., use of a standardized, established training for PRCs, collection of important study measures like PRC-participant communication logs. In the data analysis, we will confirm that the intervention is received in the same way within each intervention arm across participants and through time by comparing type and frequency of topics discussed as well as process measures (see Data Collection); we will also compare fidelity metrics by participant characteristics. In the unlikely event that we do not observe an intervention effect, participant data on social determinants, risk behaviors, patient-centered care, clinical and social services use, and technology use will be instrumental in the interpretation of study findings and recommendations for practice.

The **sample size**, N=252, was chosen to provide sufficient power for analyses associated with the defined primary outcomes and accounting for 20% attrition. In the absence of normative data, based on results of prior studies among emergency department enrolled PWUO that indicate modest uptake of MOUD (\sim 5% 191), and completing referrals to MOUD services (\sim 25% 192 194), we compute the power to detect significant effects.

Aim 2: Can the multimodal intervention be equitably implemented in clinical care?

Aim 2 is designed as a study of multi-perspective stakeholder feedback (N=50) of our proposed multimodal intervention to inform how best to integrate this approach into care teams using the RE-AIM framework to guide the evaluation of the intervention 177-179. Our sample size is driven by qualitative methods. We propose to recruit frontline providers (n=10), administrators (n=10), and a subset of PWUO participants randomized to intervention arm-1 (n=30) for a total N=50.

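### The ~80% power rests on intervention versus TAU only, but the primary hypothesis also ranks texting + PRC above texting only, a step with about 22–27% power at the plan's own rates

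*Combined protocol and SAP*

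**What the plan says.** Proposed Analyses, Aim 1, gives the primary hypothesis as an ordering: the rate of linkage, measured as time to first buprenorphine prescription, "will be highest among PWUO participants randomized to texting + PRC, followed by those randomized to texting only, then to TAU". The Study Synopsis likewise sets the three arms against one another. The analysis is a Cox model, and "Intervention group as assigned will be the sole explanatory variable in the models". No pairwise contrast, trend test or multiplicity rule is named for the ordering.

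The Cohort section says N=252 gives sufficient power for the primary-outcome analyses, allowing for 20% attrition. Its inputs are: "we anticipate that interactive texting will increase completing referrals to primary care from 25% to 35" per cent, and the combination with PRC support "will enhance time to completing referrals to primary care from 25% to 45" per cent. It continues: "These anticipated changes indicate odds ratios for intervention versus TAU (effect size) of between 1.5 to 2.0 for OUD-related outcomes". It then uses these odds ratios as a proxy for the rate ratio and reports that power for these effects, at two-sided 0.05, "using log-rank comparisons for survival outcomes via the power procedure in SAS v9.4 is ~80" per cent. Proposed Analyses repeats the sufficiency claim for N=252 without the 80% figure.

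**The concern.** The hypothesis has two steps: texting + PRC above texting only, and texting only above TAU. The power statement describes effects against TAU and does not address the first step, although its own rates fix what that effect is. A reader who sees N=252 described as sufficient for the primary-outcome analyses, next to a hypothesis that ranks all three arms, will take the ranking to be covered.

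The first step is the only one that isolates the peer coach, the component that Aims 2 and 3 go on to evaluate and cost. If the planned effects are exactly right and this contrast is tested at two-sided 0.05, roughly three trials in four will be non-significant. Without a warning in the plan, that result invites the conclusion that peer coaching adds nothing.

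**Working it through.** **Inputs.** Linkage 25% (TAU), 35% (texting only) and 45% (texting + PRC), two-sided alpha 0.05, log-rank, and 20% attrition, all from Cohort; 84 per arm from Study Design and Study Procedures. Assumptions: proportional hazards; the rates apply at the end of the 12-month follow-up; participants lost to attrition contribute no events (67.2 per arm); no multiplicity adjustment.

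**Formulas.** HR = ln(1−p2)/ln(1−p1). Events d = n(p1+p2). Schoenfeld power = Φ(|ln HR|·√d/2 − 1.96).

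**Step 1: the plan's figure, texting + PRC versus TAU.**
- HR = ln 0.55/ln 0.75 = 2.08.
- 84 per arm: d = 84 × 0.70 = 58.8; Φ(0.7315 × 7.668/2 − 1.96) = Φ(0.845) = 80.1%. Log-rank simulations give 78–79%.
- 67.2 per arm: d = 47.0; power 70.8%.

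For texting only versus TAU, HR = ln 0.65/ln 0.75 = 1.50 and power is 29.9% (84 per arm) or 24.9% (67.2 per arm). Among the pairwise contrasts, using rate-derived hazard ratios and the stated two-sided level, about 80% therefore reproduces only for texting + PRC versus TAU without attrition. The plan's 1.5 to 2.0 corresponds to these hazard ratios (1.50, 2.08); the odds ratios from the same rates are 1.62 and 2.45.

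**Step 2: texting + PRC versus texting only.**
- HR = ln 0.55/ln 0.65 = 1.388.
- 84 per arm: d = 84 × 0.80 = 67.2; Φ(0.3278 × 8.198/2 − 1.96) = Φ(−0.616) = 26.9%. Log-rank simulations give 26–28%.
- 67.2 per arm: d = 53.8; power 22.4%.

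**Step 3: other readings of the effect.** The plan's 2.0 and 1.5 versus TAU imply 2.0/1.5 = 1.33 between the two texting arms. The odds ratio for 35% vs 45% is (0.45/0.55)/(0.35/0.65) = 1.52; used as the HR, as the plan's proxy suggests, it is the most favourable reading tried.

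| HR used | 67.2 events (planned rates, 84 per arm) | All 168 participants link | Events needed for 80% |
|---|---|---|---|
| 1.33 | 21.7% | 46.2% | 380 |
| 1.388 | 26.9% | 56.5% | 293 |
| 1.52 | 40.3% | 77.4% | 180 |

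The last column is 4(1.96+0.8416)²/(ln HR)², rounded up. All three counts exceed 168, the most first events two arms of 84 can supply.

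**Step 4: precision.** With 67.2 events, SE(ln HR) = 2/√67.2 = 0.244, so the expected result is 1.39 (95% CI 0.86 to 2.24). With 53.8 events, SE = 2/√53.8 = 0.273 and the interval widens to about 0.81 to 2.37.

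**The case against.** **The printed figure is not shown to be wrong for what it describes.** The plan ties the 80% to effects against TAU, and one such comparison reproduces. This stands: the defect is an omission set beside a broader sufficiency claim. The SAS inputs are also not shown, and other routes come close to 80%. One is texting + PRC versus TAU at 67 per arm, one-sided (80.6%), although the plan says two-tailed. Another pools both texting arms against TAU with an odds ratio of 2.0 as the HR after attrition (78.4%). The sponsor should therefore confirm its inputs rather than have them assigned.

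**The plan never says it will test the two texting arms pairwise.** This is true. At 84 per arm a 2-df global test would have about 68–71% power and a 1-df trend test about 79–80%. Neither would establish that texting + PRC exceeds texting only. In simulation with both texting arms at 45% and TAU at 25%, the trend test is significant about 76% of the time, nearly as often as under the hypothesised ordering. Changing the primary test would therefore not close the gap.

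**Stronger readings that the documents do not support.**
- A reader might infer that power for the whole ordering is only about 2%. That requires both adjacent contrasts to be significant, a rule the plan does not state.
- A reader might treat 46–57% as an absolute ceiling. It holds only for HR 1.33–1.39; at 1.52 with universal linkage, power is 77%.
- A reader might set the low power against the phrase "In the unlikely event that we do not observe an intervention effect". That phrase sits in a passage on intervention fidelity and does not mention this contrast, so it needs no change on this account.

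**Conclusion.** The point holds as an undisclosed shortfall for one part of the stated primary hypothesis. Power for texting + PRC versus texting only is about 27% at the planned rates with complete follow-up and about 22% with 20% attrition. Taking the odds ratio as the hazard ratio raises it to about 40%, and no reading reaches 80%. These figures rest on proportional hazards, the plan's 25/35/45% rates, 84 per arm and an unadjusted two-sided 0.05. The trial is not powered to confirm the peer-coach step of its ordering. This does not show that the 80% is miscalculated for the comparison the sponsor had in mind, nor that the trial must fail its primary hypothesis, since the plan sets no rule for confirming the ordering.

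**What to change.** 1. In Cohort, and where Proposed Analyses repeats the sample-size claim, the sponsor should confirm the power inputs and state which comparison and attrition assumption the ~80% refers to. Add that power for texting + PRC versus texting only is about 22–27% at the planned rates (up to about 40% if the odds ratio is used as the hazard ratio), so the trial is not powered to confirm that step.
2. In the Aim 1 analysis text, report texting + PRC versus texting only as an estimate: hazard ratio with 95% CI, expected to be about 1.39 (0.86 to 2.24) with complete follow-up and wider with attrition. State that a non-significant result will not be read as showing that peer coaching adds nothing.

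The cost is wording plus one contrast from the Cox model already planned; no extra participants are needed. The downside is a less favourable stated power and a more modest claim about the peer-coach component.

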To achieve Aim 1, potential study participants with opioid use disorder (OUD) will be identified and recruited in the hospital emergency department (ED) and community settings. The study team has over two decades of experience enrolling and tracking patient participants in these high-risk communities. Each of these cohorts includes people who use opioids who are *not prescribed* any medication for opioid use disorder (MOUD), including methadone or buprenorphine, in the 30 days preceding their study enrollment.

Study settings

Planned study sites for participant enrollment will include NYC Health+Hospitals affiliated hospitals (e.g., Lincoln Hospital), the START Treatment and Recovery centers, and community settings associated with high rates of opioid overdose deaths among Black and Latinx adults in New York City.

The **study sample** of 252 Black and Latinx PWUO with a positive urine toxicology result per the Hospital EMR will be identified by the study team and approached in the ED or in community settings among PWUO self-reporting OUD and confirmed with random saliva toxicology testing and recruited over a 2-year period and followed for a duration of 12-months with purposeful recruitment of male: female adults along a 2:1 target ratio (169 males: 83 females) and a target minimum 25% aged 18-29 (see *Figure 1*). We will use venue-based and street outreach in spaces where opioid-related overdose rates are highest, and in neighborhoods where harm reduction services are located.

Potential study participants will be informed of study details by the study team, undergo informed consent, complete baseline REDCap assessment, and will then be randomized (1:1:1) using a random block design (block sizes 3, 6, 9) to 1 of 3 study arms, stratified by gender. Finally, participants will be compensated for their time at visit end and given an appointment schedule for in-person or remote survey visits. Randomly selected participants from intervention arm 1 (n=30) will be invited for the qualitative implementation interviews (see Aim 2). All randomized participants who need a phone will be provided one by the study and tracked over

time by leveraging Drs. [name]', [name]'s, and [name]'s study tracking and retention expertise in the event of changes to mobile phone numbers.

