Secondary and exploratory analysis will rely on data collected at 3-, 6-, and 12-month follow-up surveys that will permit analysis of secondary outcomes of: (1) durability of treatment effect at 52 weeks (e.g., continuous retention in OBOT with buprenorphine); (2) engagement with social services; and (3) longitudinal engagement with the proposed intervention (up to 26 weeks). For these analyses, we will use generalized linear mixed effects regression to model binary outcomes indicating longitudinal engagement in 26-week treatment (yes/no) and continuous retention in buprenorphine treatment at 3-, 6-, and 12-months (yes/no) with no more than a 28-day gap in receiving an active buprenorphine prescription over each period. These models will include a participant-specific random intercept to account for the repeated-measures structure of the data.

Methodological Considerations and Alternatives: To assess whether randomization was successful, we will compare the distribution of demographic characteristics, PhenX consensus measures, medical/psychiatric history, technology use patterns, and risk behavior variables (see *Data Collection*) by intervention arm. Variables contributing to baseline imbalance will need to be included as adjustment variables in regression models.

Missing Data and Sensitivity Analysis will rely on ensuring that the model assumption of non-informative study dropout or missing at random is reasonable and avoid potential bias, we will compare dropout rates between intervention groups as well as other measured variables, e.g., medical/psychiatric history, technology use patterns, and risk behavior variables. If there is empirical evidence of nonrandom dropout, we will model the dropout event using available factors to identify and estimate their influence. To meet missing at random model assumption, variables that predict dropout will be included as auxiliary variables via multiple imputation.

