- 1. Subjects will be enrolled and consented in person.
- All subjects will complete the following surveys before randomization (3 hours to complete): Demographic and CSDH characteristics¹⁷²; and PhenX consensus measures, including the Addiction Severity Index¹⁷⁴, Risk Assessment Battery (RAB)²⁷⁹, fatal and non-fatal overdose episodes^{177,178}, Disparate Health Care Quality¹⁷⁹, intersectional opioid-related stigma¹⁸⁰, Everyday Discrimination Scale,¹⁸¹ mobile use characteristics and Medical Outcomes Study Social Support Survey¹⁸³,

Table 2 includes REDCap survey data definitions and variables, including:

- Demographic instrument (age, race, ethnicity, veteran status, legal history, type of residence, employment, education);
- Sociocultural & demographic determinants of health;
- Clinical interview to ascertain medical and psychiatric/addiction history (family substance use history, primary, secondary and tertiary substances, pattern and severity of substance use, treatment history, individual and family medical history, current health status, prior and current medications, and psychiatric symptoms);
- Substance use and sexual risk behavior:
- Clinical and social services use; and
- 3. Participants randomized to Intervention arms-1 and 2 will have their phone numbers entered in the AI texting software dashboard. The AI-driven texting goals, operational sequences, and content have been iteratively refined in numerous studies among Black/Latinx PWUO to ensure optimal adoption (see *Table 1*)^{129,131}.

Text content are based on federal and consensus guidelines on optimizing medical management for PWUO with buprenorphine^{167,168}, and addressing CSDH^{169–171} and include:

- a. CSDH content, delivered once/day, include: (a) stigma-reduction (e.g., internalized and anticipated stigma); (b) social resources identified in our community resources & services scan (e.g., peer support groups for PWUO and other minoritized groups); (c) educational resources (e.g., GED, vocational training); (d) economic stability (e.g., public assistance, employment / vocational services, transportation vouchers); (e) food security (e.g., food stamps, food pantries, subsidized farmers markets); (f) free legal aid; and (g) emergency housing.

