In Aim 1, all participants will be assigned a survey ID accompanied by their phone number and name. This master-list survey database will be stored in a password protected FRI server. Participant data will be stored in REDCap and will be accessible only to members of the research staff. Data analysis will be automated as much as possible. As there is negligible transcription of data, errors in data entry introduced by experimental staff should be minimal. When data must be entered by hand (for example during focus group sessions), data will be double-entered and checked for accuracy using standard data shells. Our proposed analysis will use all available data, under an intent-to-treat principle. As a first step, we will generate descriptive statistics to characterize the sample at baseline on sociodemographic, health and psychiatric symptoms, substance use, and technology use characteristics, both overall and by intervention group (texting + PRC vs. texting only vs. TAU). Descriptive statistics include means, standard deviations, percentiles, and frequencies with percentages, as appropriate. Then, in support of Aim 1, we will investigate the impact of the three-arm intervention on primary outcomes. To assess these hypotheses (see Data Analysis, Aim 1), we will utilize the Cox regression model to investigate whether there are differences in time to service linkage (in weeks) by intervention group. Cox regression is a method for investigating the effect of several variables upon the time to a specified event. Data collected at 3-, 6-, and 12-month follow-up surveys as well as from the participant EHR will permit analysis of secondary outcomes of engagement in intervention and durability of treatment effect. For these analyses, we will use logistic regression to model binary outcomes indicating longitudinal engagement in 26-week treatment (yes/no) and continuous retention in primary care-based buprenorphine treatment at 3-, 6-, and 12-months (yes/no) with no more than a 28-day gap in receiving an active buprenorphine prescription over each period. To assess whether randomization was successful, we will compare the distribution of demographic characteristics, PhenX consensus measures, medical/psychiatric history, and technology use patterns (see Data Collection) by intervention arm. Variables contributing to baseline imbalance will be included as model adjustment variables. To ensure that model assumption of non-informative censoring/study drop out is reasonable and avoid potential bias, we will compare dropout rates between intervention groups as well as other measured variables, e.g., demographic, social determinants, and risk behavior variables. If there is empirical evidence of nonrandom dropout, we will model the dropout event using available factors to identify and estimate their influence.

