We realize that there is potential for a participant to enroll in the study more than once if protections are not put in place to prevent, or at least minimize, this occurrence. To begin with, all participants will be asked for identification and in the event that a participant does not have ID, other items that include name and birth date such as the Benefits ID card, medical documents, birth certificate, voter registration, court papers, etc. will be accepted if accompanied by a picture ID that shows the participant's name and photo (student ID, employment ID, etc.). In addition, personal identifying information such as birth date and

mother's maiden name will be collected at enrollment and research staff will log this information into a password protected database that will be updated into a master list of participants enrolled every day. Prior to enrollment, participants' names will be checked in this master database. While these efforts may not fully protect against duplicate enrollment, we feel it will greatly minimize this occurrence and potential bias.

Approximately 5% of sessions from each intervention arm will be randomly selected to be audio-recorded. Participants will sign a separate consent form to agree to this recording. If a participant declines, the next randomly selected individual will be recorded. To ensure the quality and integrity of the randomization, it is important to minimize contamination across conditions. Therefore, we will (1) schedule in-person study visits in a private room or space to ensure conversations are not overheard; (2) reduce the potential for overlap of participants assigned to different arms by scheduling only one study arm on a particular day; and (3) assess potential contamination by asking participants if they heard about the study prior to entry, if they know anyone who has participated in the study and compare these instances by study arm. Our past work indicates that contamination is unlikely. However, if a participant reports knowing others in the study, they will be asked to share the individual's name so that a variable can be created that indicates potential contamination which will be considered in the analysis.

Collection and Reporting of SAEs and AEs

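### The primary Cox model for Aim 1 is not fixed: an imbalance rule with no criterion can add covariates, and no section says which fit is then primary

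*Combined protocol and SAP*

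**What the plan says.** Proposed Analyses (Aim 1) specifies Cox regression for time to linkage: "Intervention group as assigned will be the sole explanatory variable in the models". The same sentence refers the reader to Methodological Considerations and Alternatives.

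That section compares the arms on "demographic characteristics, PhenX consensus measures, medical/psychiatric history, technology use patterns, and risk behavior variables" and continues: "Variables contributing to baseline imbalance will need to be included as adjustment variables in regression models". Data Entry & Analysis repeats the rule after its Cox and logistic regression text: "Variables contributing to baseline imbalance will be included as model adjustment variables". Its list of compared variables leaves out the risk behaviour family. The families are broad: Study Procedures, Day 0, speaks of "PhenX consensus measures, including the Addiction Severity Index" among several other instruments.

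The Quality Assurance Plan adds that, where participants know each other, "a variable can be created that indicates potential contamination which will be considered in the analysis". It does not say which analysis. The power statement under Cohort was computed "using log-rank comparisons for survival outcomes via the power procedure in SAS v9.4" and mentions no covariates.

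Study settings randomises participants "to 1 of 3 study arms, stratified by gender", and the enrolment and recruitment sections repeat this. No Aim 1 analysis section names gender as a stratum or covariate.

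**The concern.** A primary analysis should be identifiable before the data are seen. Here the covariate set depends on a baseline comparison whose criterion is unstated, so two analysts following the text faithfully could fit different models. After randomisation any baseline imbalance is chance by construction. Choosing covariates because they are imbalanced, and not because they predict linkage, gives no assurance of better precision. If the rule adds a variable, the trial has an unadjusted and an adjusted result, and nothing ranks them. The two can fall on opposite sides of p=0.05, and they can give different hazard ratios.

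Gender is a smaller matter. The design balances it, but the model does not use it, and the imbalance rule cannot be relied on to bring it in.

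**Working it through.** **1. The plan's own figure.** For arm 1 versus TAU, Cohort gives 25% and 45%, with 252/3 = 84 per arm.
- HR = ln(1−0.45)/ln(1−0.25) = 2.078; events = 84 × (0.25+0.45) = 58.8.
- Schoenfeld: z = √(58.8/4) × ln 2.078 − 1.96 = 0.84, so power is 0.801.

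The stated ~80% is therefore matched by an unadjusted comparison of these two arms with no attrition. With 67 per arm after 20% attrition it is 0.707. That shortfall is a separate matter. What counts here is that the figure describes an arm-only analysis.

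**2. How often the rule could fire.** For k independent candidates tested at p<0.05, the chance of at least one flag is 1 − 0.95^k:

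| k | 5 | 10 | 20 | 30 | 40 |
|---|---|---|---|---|---|
| Chance | 23% | 40% | 64% | 79% | 87% |

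Table 2 names about 30 baseline items or scales besides gender, by my count (14 sociodemographic, 12 substance use and health, 4 psychological or physical), so 20 to 40 was taken as the range. Simulation gave 64–88% for independent candidates and 42–59% with pairwise correlation 0.5. With 10 candidates at that correlation it was about 30%. If the criterion is a largest pairwise standardised difference above 0.2, a flag is practically certain.

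**3. What follows when it fires.** Set-up:
- From the plan: 169 men and 83 women, blocks of 3/6/9 within gender, linkage of 25/35/45% at 12 months, 20% dropout (about 80 events in all).
- Assumed: exponential times; 20 or 40 normal candidates; correlation 0 or 0.5; and three effect settings. These were no effects; women's HR 0.5; and women's HR 0.7 with five prognostic candidates at HR 1.3 per SD.
- 4,000 trials in each of the 12 combinations, repeated under the null (25% in every arm, about 57 events).

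Results for arm 1 versus TAU:

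| Flag (assumed) | Mean number added, 20/40 candidates | Fits disagree on p<0.05: independent; correlated | Type I error, rule fixed in advance |
|---|---|---|---|
| p<0.05 | 1.0/2.0 | 2.5–4.8%; 1.8–8.1% | 0.040–0.052 |
| p<0.10 | 2.0/4.0 | 4.1–6.7%; 2.8–11.2% | 0.041–0.053 |
| difference >0.2 | 8.0/16.0 | 7.3–11.3%; 5.6–13.2% | 0.049–0.061 |
| difference >0.1 | 15.9/31.8 | 8.5–13.5%; 7.8–15.3% | 0.057–0.081 |

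The Monte Carlo standard error of a 5% rate is √(0.05×0.95/4000) = 0.34 points. Correlation lowers disagreement when candidates are not prognostic and raises it when they are. Power with the p<0.05 rule moved by −1.7 to +1.4 points against the unadjusted fit. Clear gains appeared only with prognostic candidates.

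The estimate moves too. In a second set of 3,000-trial runs (10 candidates, three prognostic at log-HR 0.4 per SD, women's HR 0.6, true HR 2.078), the median HR was 1.91 arm-only, 1.92 with the p<0.05 rule and 2.02 with a difference >0.1 rule.

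**4. Gender.** It was flagged in 0 of 96,000 trials (largest standardised difference 0.076). Unadjusted and gender-stratified results, 16,000 runs per effect setting:
- Power: 0.745/0.744 (no effects), 0.748/0.759 (women's HR 0.5), 0.753/0.755 (women's HR 0.7 plus prognostic candidates).
- Type I error: 0.045/0.045, 0.042/0.044, 0.048/0.048.

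**The case against.** The strongest reply is that the text forms one conditional rule: arm only, unless imbalance is found, then adjust. This largely stands. A reader might infer two contradictory primary models, but the sole-variable sentence itself points to the section with the rule, and the log-rank power basis is ordinary and fits an arm-only default. What survives is narrower: the trigger is undefined, and the standing of the unadjusted fit after triggering is unstated. The word Alternatives in the section title does not settle it, because the wording of the rule is mandatory in both places and neither calls the adjusted fit secondary.

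A second reply is that the effect is small. With a p<0.05 flag the fits agree in about 92–98% of simulated trials. The larger disagreement comes from standardised-difference rules that add 8 to 32 covariates on average to a model with about 80 events, which few analysts would call primary. That is fair, although the plan does not exclude such a rule.

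Third, the contamination variable sits in the quality assurance text, which does not mention the primary model. That also stands; it needs only a label.

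Fourth, putting gender in the model is partly preference. Naming the arm-only fit as primary would also end the ambiguity. In addition, Inclusion of Women and Minorities excludes nobody on gender identity, so a sparse third stratum is possible, and only two strata were simulated.

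**Conclusion.** The concern holds as an unfixed primary model with a modest consequence. How often the rule fires and how often the fits disagree rest on assumed thresholds, candidate numbers, correlations and covariate effects, none of which the documents give.

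Three stronger conclusions are not supported:
- A reader might infer that the rule would be triggered in most trials. The plan states no criterion, and plausible inputs give rates below one half (42% with 20 correlated candidates, 23% with five independent ones).
- A reader might infer inflated type I error. A p-value flag fixed in advance stays near 5%. Only the loosest standardised-difference rule clearly exceeds it. If the more favourable of the two fits were always reported, the mean rate would be 0.051 (p<0.05 flag), 0.055 (p<0.10) or 0.067 (difference >0.2), against 0.045 unadjusted. These are upper bounds, and no section says the choice would be made that way.
- A reader might infer that omitting gender invalidates the test. It does not; the omission is at most slightly conservative.

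**What to change.** - **Proposed Analyses (Aim 1):** replace the sole-variable sentence with a Cox model for assigned arm, stratified by gender as categorised in the randomisation list, and state that this fit alone is primary. Keeping the arm-only fit as the sole primary fit is an acceptable minimal alternative.
- **Methodological Considerations and Alternatives; Data Entry & Analysis:** report baseline balance descriptively, and label any imbalance-adjusted fit as a sensitivity analysis. If the stratified model is adopted, give the unadjusted Cox or log-rank result the same label.
- **Quality Assurance Plan:** label any fit using the contamination variable as a sensitivity analysis.

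No new data are needed, since gender must be known at randomisation and is recorded on the screening log. Stratifying changes power by about −0.1 to +1.1 points with two strata. The cost is a protocol wording change, including to the primary model if stratification is chosen. Under Reporting mechanisms of IRB actions to NIDA, a change decided by the investigator must be communicated to the funder before it is implemented.
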